### STATISTICAL ANALYSIS

The primary end point was the percentage of patients in each group with a Perlas grade 2 antrum. Based on an estimated prevalence of full stomach in fasting patients scheduled for elective surgery of approximately 5%, and a prevalence of gastroparesis in DM patients of around 15%, 141 patients per group would be required, assuming an alpha risk of 0.05 with a power of 80%. To account for an anticipated attrition rate exceeding 5%, we aimed to include a total of 296 patients (148 per group). Continuous data were presented as mean plus standard deviation (SD) for normally distributed data, and median plus interquartile

range (IQR) for nonnormally distributed data, after assessment of normality using the Shapiro-Wilk or Kolmogorov-Smirnoff test. Categorical variables were summarized as counts and percentages and were compared with a  $\chi^2$  test or Fisher exact test when appropriate. Group comparisons between patients with or without gastroparesis were performed using Student *t* test or the Mann-Whitney test as appropriate. Subgroup analyses were performed using 1-way analysis of variance (ANOVA), with post hoc Tukey-Kramer's method for pairwise subgroup comparison in the event of a positive ANOVA result. Alternatively, the Kruskal-Wallis test was used when ANOVA assumptions were not met, with the Dunn test for subgroup comparison in cases of a positive Kruskal- Wallis test result.

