**METHODS:** Prospective, observational, single-blinded study. All adult patients, both those with DM and those without, who were scheduled for elective surgery under general or regional anesthesia, underwent assessment for eligibility to participate in the study. Written informed consent was obtained from all participants before enrollment. The inclusion criteria were as follows: body mass index (BMI)  $<40 \text{ kg.m}^{-2}$ ; age  $\geq 18$  years; ASA physical status I to III; individuals undergoing elective surgery who had the ability to understand the study rationale and provide informed consent. Exclusion criteria included pregnancy, recent upper gastrointestinal bleeding ( $<1$  month), abnormal anatomy of the upper gastrointestinal tract (such as hiatal hernias and gastric tumors), prior surgical procedures on the esophagus, stomach, or upper abdomen, gastroesophageal reflux disease, nondiabetic autonomic-neurological diseases, chronic kidney diseases, and previous use of prokinetics or opioids. Participants satisfying the inclusion criteria were consecutively enrolled as permitted by surgical programming and availability of research team members and were distributed in 2 groups (DM patients and controls) in a 1:1 ratio. According to the standard institutional practice, all patients underwent an 8-hour fasting period without solids and a 2-hour period without clear liquids before their scheduled elective surgery. Patients were permitted to take their regular morning medications with a sip of water 1 hour before the surgery. DM patients underwent an evaluation for the duration of DM, medication history, glycemic control assessed by glycosylated hemoglobin (HbA1c) levels, and symptoms of gastropathy (such as bloating/ abdominal distension, early satiety/postprandial fullness, nausea/vomiting, or abdominal pain/ discomfort). Additionally, other DM-related complications including diabetic nephropathy, diabetic retinopathy, diabetic vascular disease, and the presence of cardiovascular autonomic neuropathy (CAN; as an indicator of gastric dysautonomia) were documented for analysis. Patient demographics, ASA physical status, and treatments were also collected. During preoperative evaluation, assessment of

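### The diabetic versus non-diabetic comparison is unmatched and unadjusted, so a crude difference, or the lack of one, may partly reflect age, sex or body size; prespecify a short adjusted model beside the crude test

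*Combined protocol and SAP*

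**What the plan says.** The METHODS section describes a prospective observational study. Eligible patients "were consecutively enrolled as permitted by surgical programming and availability of research team members and were distributed in 2 groups", DM and controls, 1:1. The ratio fixes the group sizes; no matching or stratification variable is named. Eligibility does restrict the population: adults with BMI below 40 and ASA class I to III having elective surgery. Reflux disease, abnormal upper gastrointestinal anatomy or previous surgery there, chronic kidney disease, non-diabetic autonomic disease, and prokinetic or opioid use are all excluded.

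On covariates, the same section says: "Patient demographics, ASA physical status, and treatments were also collected". Age is also needed for the volume formula, and BMI is needed to apply the eligibility limit.

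The STATISTICAL ANALYSIS section says: "The primary end point was the percentage of patients in each group with a Perlas grade 2 antrum". On tests it says: "Categorical variables were summarized as counts and percentages and were compared with a" χ² or Fisher exact test. Continuous outcomes get a t or Mann-Whitney test for two groups, and one-way ANOVA or Kruskal-Wallis with post hoc comparisons for subgroups. The section contains no regression, covariate list, stratified analysis, propensity method or sensitivity analysis.

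**The concern.** The title and background set diabetic patients against controls and give delayed gastric emptying as the reason diabetics are thought to be at risk. A reader will want to know whether diabetes, with or without dysautonomia, accounts for any difference in full-stomach prevalence. Groups formed by consecutive enrolment can differ in age, sex and BMI, and eligibility limits narrow those ranges without balancing them: age is open from 18 upward and BMI anywhere below 40. With only crude tests, neither a positive nor a null result can be separated from such differences. The variables needed to do so are collected but have no role in the comparison. A larger sample would not cure this.

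**Working it through.** **1. The plan's own sample size.** Inputs from STATISTICAL ANALYSIS: 5% versus 15%, alpha 0.05 (taken as two-sided), power 80%. With pooled variance and no continuity correction:

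n = [1.960·√(2·0.10·0.90) + 0.842·√(0.05·0.95 + 0.15·0.85)]² / 0.10² = 140.1, rounded up to 141.

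The stated 141 per group reproduces (power 80.3%). It is the size for a crude two-proportion test, with no allowance for covariates.

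**2. How far a confounder could move the primary comparison.** These inputs are assumptions, not document values: one normally distributed confounder whose mean is d SD higher in the DM group, an odds ratio OR per SD for grade 2, and no diabetes effect. The logistic intercept is set so that controls average 5% (−3.018 for OR 1.5; −3.155 for OR 2.0). The DM rate p₁ is the average of expit(intercept + ln(OR)·x) with x centred at d. Rejection is for the pooled two-sided 5% test with 141 per group.

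| d (SD) | OR per SD | DM rate | Rejection |
|---|---|---|---|
| 0.5 | 1.5 | 6.05% | 6.7% |
| 0.5 | 2.0 | 6.9% | 10% |
| 1.0 | 1.5 | 7.3% | 13% |
| 1.0 | 2.0 | 9.3% | 29% |

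Last row written out: the difference is 0.0932 − 0.05 = 0.0432, the null standard error is 0.0307 and the alternative standard error is 0.0306. Then (0.0432 − 1.960·0.0307)/0.0306 ≈ −0.55, so the upper tail gives about 29%. A confounder acting the other way would pull the DM rate down and could hide a real difference.

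**3. Age in the volume outcome.** The formula under Ultrasound Assessments is GV = 27.0 + 14.6·CSA − 1.28·age. At equal CSA, a DM group 10 years older has a mean GV lower by 1.28 × 10 = 12.8 mL. The 10 years is an assumption; the coefficient is the plan's. With an assumed GV SD of 25 to 45 mL and 141 per group, the standard error is SD·√(2/141), or 2.98 to 5.36 mL. A gap of that size alone would be significant in about 99% to 67% of studies.

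**4. CSA and GV under age adjustment.** Substituting the formula into a linear model that contains age changes the age coefficient by −1.28 and multiplies every other slope by 14.6. The adjusted GV contrast is therefore exactly 14.6 times the CSA contrast, with the same p-value (formula applied as written, without truncation).

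**5. What the data can carry.** Expected grade 2 events at the plan's rates are 0.05·141 + 0.15·141 = 7.05 + 21.15 = 28.2. A model with DM status, age, BMI and sex has four slopes, about 7 events each. A three-level group makes five, about 5.6 each. With 5% in both groups there would be 14.1 events in all.

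**6. Price in precision.** With n/(1 − R²), where R² is the assumed share of DM status explained by the covariates: R² = 0.10 gives 141/0.90 = 156.7, or 157 per group; R² = 0.20 gives 141/0.80 = 176.3, or 177. The plan enrols 148. Equivalently, the interval widens by 1/√0.90 = 1.05 to 1/√0.80 = 1.12. For scale, a single covariate shifted by 1.0 SD has R² = d²/(d² + 4) = 0.20.

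**The case against.** Several points on the other side have force.

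- **The stated outcome is a prevalence.** The OUTCOMES section speaks of assessing how common a full stomach is, and the endpoint is a percentage in each group. For whether diabetics, as they present for surgery, more often have a full stomach, the crude contrast is legitimate. This stands, and it is why the crude test should stay. It does not cover attribution to diabetes or dysautonomia, which the background invites.
- **The plan does restrict.** The BMI and ASA limits and the exclusions remove several rival explanations. It would be wrong to say that nothing was done about confounding; what is missing is balance or adjustment within those limits.
- **The size is assumed.** The 6.7% rejection at the bottom of the range is close to nominal, and 29% needs both extreme assumptions at once. The middle cases are 10% and 13%.

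A reader might infer more: that diabetics in this study are older and heavier, so the crude test will produce a spurious diabetes effect. The documents do not support that. They give no baseline figures and no link between age or BMI and grade 2. Nor does the volume formula supply one. Age enters only when CSA is converted to GV, a secondary outcome, while the Perlas grade is a visual grade with no age term. The age term is also negative, so an older diabetic group would get a lower GV at equal CSA, which would tend to mask a difference.

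**Conclusion.** The point holds in a limited form. Matching and stratification are absent, every listed comparison is unadjusted, and the collected covariates go unused. A crude difference, or its absence, may therefore partly reflect age, sex or body size, in an unknown direction. The only size that can be given for the primary endpoint rests on assumed confounder strength: a DM rate of about 6.05% to 9.3% against 5% with no diabetes effect, and rejection in about 7% to 29% of studies. For GV, the plan's own coefficient gives 12.8 mL per assumed 10-year age gap. The sample size arithmetic is correct for the crude test and is no evidence either way. This should be fixed and is cheap to fix, but the crude prevalence comparison is not invalid.

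**What to change.** 1. Keep the χ²/Fisher result as the crude comparison of prevalence.
2. Prespecify beside it a Firth-penalised logistic regression of grade 2 on DM versus non-DM, with age, BMI and sex. Report the adjusted odds ratio and the standardised risk difference, each with a 95% CI. Base any statement attributing a difference to diabetes on this model.
3. Fit the three-level group (non-DM, DM-NDYS, DM-DYS) as a secondary model, given about 28 expected events, and keep the covariate list this short.
4. For the continuous outcomes, fit one linear model for CSA adjusted for age, BMI and sex. If the adjusted GV contrast is also reported, present it as the CSA contrast multiplied by 14.6 and not as a separate test.
5. State that the 80% power refers to the crude comparison.

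The cost is SAP wording and a few models on data already collected. The real downside is a wider interval. Its size depends on how strongly the covariates predict diabetes status: an assumed R² of 0.10 to 0.20 corresponds to about 157 to 177 per group for the same precision, against 148 planned.
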